12.9.2 Descriptive Analyses

12.9.2.1 Attrition diagram

An attrition diagram will be created, describing the number of records excluded from the statistical analyses, by reason of exclusion.

12.9.2.2 Descriptive analysis of demographics and baseline characteristics of included patients

We will describe the demographic and clinical characteristics of the patients both overall and by respiratory pathogen. Counts and proportions (% along with 95% exact binomial confidence intervals) will be presented for several variables, including age group, sex, diagnosis, symptoms, chronic conditions, vaccination status and residence in long-term care facilities.

Euler diagrams will be used to visually represent the overlap in pathogen detection across specimen types. In the SAP, visualization and presentation of results will be further defined.

12.9.3 Data Analysis

12.9.3.1 Detection rates of respiratory pathogens

Positive laboratory results for each respiratory pathogen of interest will be reported by specimen type. This includes nasopharyngeal swabs, saliva, blood, and sputum. Serology is considered positive for recent infection if a fourfold or greater rise in virus-specific IgG antibodies is observed between paired samples. If all samples (respiratory and blood samples) collected in the time frame are negative, the patient is considered as not having any laboratory-confirmed infection.

For each specimen type, the percentage of positive diagnoses will be calculated by dividing the number of patients in whom the pathogen was detected using that specimen (alone or in combination) by the total number of included patients. Detection rates in sputum and blood samples will be calculated by dividing the number of patients in whom the pathogen was detected using that specimen (alone or in combination) by the total number of included patients who provided sputum or blood samples.

Comparative detection rates will be assessed by calculating the percentage increase in positivity when additional specimen types are included, using nasopharyngeal as the reference. This will allow evaluation of the incremental diagnostic value of each specimen type.

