 - Influenza detection rates (%) by Influenza vaccination status (vaccinated in the last 12 months or not vaccinated in the last 12 months).

Exploratory objectives:

5. To assess the detection rates (%) of co-infections (all pathogens tested) in adult (s)ARI patients (≥ 18 years), when using multi-specimen collection compared to a single nasopharyngeal swab, overall and by additional specimen type.
 - And stratify by disease severity (PCC, ED ward, hospitalization, death), if the sample size allows.
6. As primary objective, stratified by subtype or serotype (when applicable)
 - RSV detection rates by RSV subtype A and B
 - PIV detection rates by PIV serotype (1-4)
7. To assess the detection rates (%) of Influenza, SARS-CoV-2 and other viral pathogens tested for with the RT-PCR multiplex panel in adult (s)ARI patients (≥ 18 years), when using multi-specimen collection compared to a single nasopharyngeal swab, overall and by additional specimen type.

Study design:

Multi-setting (inpatient, ED ward and PCC) prospective cohort study of (s)ARI cases

Study duration:

Recruitment period: 7th of January 2026 – 30th of June 2026. Sample collection between 7th of January 2026 and 31st of July 2026.

Inpatient setting: baseline samples to be taken within 48 hours of hospital admission, as soon as possible after admission. Convalescent blood sample to be taken between 25 and 31 days after hospital admission.

ED and PCC setting: baseline samples to be taken within the initial consult.

Population, setting and eligibility criteria:**Study setting:**

A pilot study will be conducted in one (1) hospital ([name], Valencia), one (1) ED ward ([name], Valencia), and up to four (4) PCC, all based in Valencia, Spain.

Study participants: Patients are included if they are:

- Adults aged 18 years and older
- AND
- Meet the (s)ARI case definition
- AND
- Willing to have a nasopharyngeal and oropharyngeal swab collected as well as saliva. Sputum and serology are optional and will be consented for on the informed consent form (ICF) as separate items.
- AND
- Willing and able to provide informed consent, obtained from the patient or from the patient's Legally Acceptable Representative(s).

Individuals (patient) cannot be enrolled if:

- patient cannot be swabbed due to severe septum deviation, obstruction, or other conditions that contra-indicate swabbing,
- patient was previously enrolled in the study within 30 days of their current visit/admission,

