12.3.1 Case definition

For the purposes of this study, the case definition of (s)ARI will serve as the main definition for identifying cases across all healthcare settings involved—hospitals, PCC, and ED. Recognizing that the classical (s)ARI definition includes hospitalization as a criterion, which is not applicable in PCC and ED contexts, we will adopt the notation (s)ARI to reflect that not all patients have severe illness. The presence of the same symptoms will be used to trigger enrolment in the study in all settings.

A (s)ARI case is defined as a patient with a suspicion of a respiratory infection with at least one of the following symptoms:

- cough
- fever (≥ 38 C°)
- shortness of breath
- sudden onset of anosmia, ageusia, or dysgeusia

with symptom onset within the last 14 days prior to hospital admission and symptoms occurring for at least 24 hours.

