12.3.3 Exclusion Criteria

Individuals (patient) cannot be enrolled if:

- patient cannot be swabbed due to severe septum deviation, obstruction, or other conditions that contra-indicate swabbing,
- patient was previously enrolled in the study within 30 days of their current visit/admission,
- patient develops signs and symptoms of (s)ARI after being hospitalized.

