12.5 Variables

12.5.1 Outcome(s)

12.5.1.1 Primary Outcome – Laboratory-confirmed respiratory infection

A laboratory-confirmed respiratory infection is defined as either:

- a positive RT-PCR result from the nasopharyngeal, oropharyngeal, sputum or saliva respiratory sample, and/or
- a positive serology result from paired blood samples (hospitalized patients only).

The outcome of interest for the primary objectives is a laboratory-confirmed infection with one of the viral respiratory pathogens of interest:

- RSV:
 - Subtype A
 - Subtype B
- PIV
 - Serotype 1
 - Serotype 2
 - Serotype 3
 - Serotype 4
- hMPV

The RT-PCR commercial kit will be used on the nasopharyngeal, oropharyngeal, sputum or saliva respiratory samples and will test for additional pathogens as well including Influenza A and B and SARS-CoV-2.

There will be no results for these additional pathogens on the blood samples.

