12.7 Study Procedures

Patients attending to PCC, ED and patients hospitalized will be screened to select eligible (s)ARI patients¹. These patients will be approached for written informed consent. Those willing to participate in the study will be asked to provide saliva, nasopharyngeal swabs and oropharyngeal swabs, with optional sputum samples. Blood samples are collected only from hospitalized patients, with paired serology used to confirm recent infection. Study samples will be collected by trained personnel following instructions for proper identification, hygiene procedures, and sample labelling which will be outlined in the Study Assessments and Procedures form.

No treatment is provided as part of this study; routine clinical management and standard-of-care therapies will be provided to the study participants.

The following samples are taken to identify the pathogen causing the respiratory infection:

Table 2. Sample collection by setting

Sample type	ED and PCCs setting	Hospitalized
Nasopharyngeal	Required	Required
Oropharyngeal	Required	Required

¹ In the hospital setting, during January and February a maximum of 100 patients per month will be consecutively recruited during the week (Monday to Friday). During the other months with expected high hMPV and PIV circulation, all (s)ARI patients will be approached (including weekends). For both the ED ward and PCC setting, (s)ARI patients will be recruited consecutively during the week (Monday to Friday). Each week 12 (s)ARI patients will be recruited per setting. During the peak season of respiratory illnesses, the targets will be reached before Friday after which recruitment will be halted for that week. In slower recruitment weeks, all patients will need to be approached to reach the target sample size of 12 (s)ARI patients.

Sample type	ED and PCCs setting	Hospitalized
Saliva	Required	Required
Sputum (optional)	Optional	Optional
Blood sample taken at baseline in hospital (optional)	Not collected	Optional
At convalescence: Blood sample taken 28 (+/- 3 days) days after hospital admission (if baseline sample was taken)	Not collected	If baseline is taken

Respiratory samples

A laboratory-confirmed infection is a positive multiplex RT-PCR on a respiratory sample collected between hospital admission and up to 48 hours after hospital admission, preferably as soon as possible. For ED/PCC patients, sample should be collected at time of the initial visit.

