All respiratory samples (nasopharyngeal, oropharyngeal, sputum and saliva samples) will be tested using a commercial RT-PCR kit, which has undergone quality and/or validation processes. Study Contributor will be requested to submit validation logs summarizing the quality check process, results, timing and certificates of analysis for assays performed.

Blood samples

Blood samples will be collected only from hospitalized (s)ARI patients. A baseline sample is taken at admission (within 48 hours), and a convalescent sample is requested 28 days (+/- 3 days) after hospital admission. If the patients have already been discharged from the hospital for the second blood sample, a study nurse will visit them at their homes to collect the required samples and information or transport will be arranged for the study participant to come to the hospital. The serum sample must be stored and transported at -20°C. Every month a batch of blood samples will be transported to the central laboratory in Lyon, France. Whenever possible, blood taken as part of the standard of care will be salvaged for this study.

[figure not shown]
ELISA technique will be used to detect and quantify IgG antibody titers. The following antibody titers will be tested:

- RSV-A IgG antibody titers baseline
- RSV-A IgG antibody titers convalescence
- RSV-B IgG antibody titers baseline
- RSV-B IgG antibody titers convalescence
- hMPV-A IgG antibody titers baseline
- hMPV-A IgG antibody titers convalescence
- hMPV-B IgG antibody titers baseline
- hMPV-B IgG antibody titers convalescence
- PIV1 IgG antibody titers baseline

- PIV1 IgG antibody titers convalescence
- PIV2 IgG antibody titers baseline
- PIV2 IgG antibody titers convalescence
- PIV3 IgG antibody titers baseline
- PIV3 IgG antibody titers convalescence
- PIV4 IgG antibody titers baseline
- PIV4 IgG antibody titers convalescence

See Figure 1 for the schematic overview of the samples that will be taken and the test to be performed.

Figure 1. Study procedure overview

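### An infection acquired between the two blood draws is scored as a nasopharyngeal miss and can inflate the exploratory serology gain

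*Protocol*

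**What the plan says.** Serology positivity is fixed in Protocol Section 12.9.3.1: "Serology is considered positive for recent infection if a fourfold or greater rise in virus-specific IgG antibodies is observed between paired samples". Under Section 12.5.1.1, positive paired serology in a hospitalised patient is enough by itself for a laboratory-confirmed infection; RT-PCR need not be positive as well. Section 12.9.3.1 then measures the gain from each added specimen against the nasopharyngeal swab.

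The two kinds of evidence cover different periods. Section 12.7 says of RT-PCR: "A laboratory-confirmed infection is a positive multiplex RT-PCR on a respiratory sample collected between hospital admission and up to 48 hours after hospital admission". It says of blood: "A baseline sample is taken at admission (within 48 hours), and a convalescent sample is requested 28 days (+/- 3 days) after hospital admission".

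The illness under study is the one that brought the patient in. The case definition in Section 12.3.1 applies to patients "with symptom onset within the last 14 days prior to hospital admission and symptoms occurring for at least 24 hours".

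Section 12.9.1 expects serology from 150 patients and calls that analysis exploratory, with limited power. Section 12.12 admits false-positive serology and gives cross-reactivity as the example.

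**The concern.** The swab describes the patient in the first two days. The antibody rise describes the following three to four weeks as well. A patient admitted with some other illness may catch RSV, hMPV or PIV on the ward or at home, early enough to show a fourfold IgG rise by the second draw. The rule counts that patient as serology-positive and nasopharyngeal-negative, yet no baseline swab could have found an infection that had not yet occurred.

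Through this mechanism the error can only add to the multi-specimen side. Exposure between the draws is foreseeable: Section 12.4 has all inpatients approached after February because high hMPV and PIV circulation is expected. No section of the protocol describes a record of new respiratory illness between the draws or an analysis that sets such rises aside. If the information is not collected at the convalescent contact, a later SAP cannot recover it.

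**Working it through.** **Inputs from the protocol (Section 12.9.1).** 150 patients with serology; total N about 1,074; a doubling of detection at incidence 1% to 7%; stated 95% half-widths on the gain of ±0.6 to ±1.8 percentage points.

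**Inputs assumed, not in the protocol.** Six-month infection risk r per virus of 2%, 5% or 10%, spread evenly over 182 days; a window d of 11, 17 or 21 days after admission in which a new infection can still give a rise by the second draw; every such infection gives a fourfold rise.

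**1. The plan's own figure.** Half-width = 1.96 × √(g(1 − g)/1,074), where g is the gain. At g = 1% this is 0.60 points, as stated. At g = 7% it is 1.53, not 1.8; the value 1.79 belongs to g = 10%. That mismatch is a separate matter and does not affect this point.

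**2. Gain in the serology subset if detection doubles.** 150 × 1% = 1.5 extra cases; 150 × 7% = 10.5 extra cases. With n = 150 and a 1% gain the half-width is 1.59 points, or 150 × 1.59% = 2.4 cases.

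**3. Expected infections between the draws, per virus.** E = 150 × r × d/182.

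| Window d | r = 2% | r = 5% | r = 10% |
|---|---|---|---|
| 11 days | 0.18 | 0.45 | 0.91 |
| 17 days | 0.28 | 0.70 | 1.40 |
| 21 days | 0.35 | 0.87 | 1.73 |

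For the assumed risks these are upper bounds, because not every infection gives a fourfold rise in time.

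**4. Against the gain, at 17 days.** At 1% incidence: 0.28/1.5 = 19% to 1.40/1.5 = 93%. At 7%: 0.28/10.5 = 3% to 1.40/10.5 = 13%. Pairing low risk with low incidence gives 19%; pairing high with high gives 13%.

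**5. Cross-check on the ratio scale.** Let p be the nasopharyngeal rate, 2p the true multi-specimen rate, and q the chance that a patient without the virus at baseline acquires it and shows a rise. The table above implies q from 2% × 11/182 = 0.12% to 10% × 21/182 = 1.15%. Apparent ratio = (2p + (1 − 2p)q)/p; the true ratio is 2.

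| p | q = 0.1% | q = 0.5% | q = 1% |
|---|---|---|---|
| 1% | 2.10 | 2.49 | 2.98 |
| 7% | 2.01 | 2.06 | 2.12 |

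Extra positives, 150 × (1 − 2p) × q, are 0.15, 0.73 and 1.47 at p = 1%, in line with step 3.

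**6. Against the whole study.** 0.18/1,074 = 0.02 points and 1.73/1,074 = 0.16 points, compared with the stated ±0.6.

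**The case against.** The strongest reply is that the effect is about one patient per virus, in 150 patients, in an analysis already called exploratory. Even 1.73 patients is less than the 2.4-case half-width in that subset, and over the full sample it is at most 0.16 points. The doubling in Section 12.9.1 is set for the combined sample with one added specimen, so using it as the yardstick for the serology subset is this review's choice. All of that stands. It limits the weight of the point without removing it, since serology still enters the primary outcome definition and a bias does not average out as sampling error does.

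A reader might infer three stronger things that the documents do not support.

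- **That the endpoint contradicts the exclusion criterion** "patient develops signs and symptoms of (s)ARI after being hospitalized". That criterion acts at enrolment and says nothing about an eligible patient infected later. What such an infection falls outside is the case definition, which requires onset before admission.
- **That up to 90% of the gain could be artefact.** That sets the highest assumed risk against the lowest incidence for the same virus in the same months, an unlikely pairing.
- **That the serology gain is biased upward overall.** Onset may precede admission by up to 14 days and blood may be taken up to 48 hours after it, so IgG can already be raised at baseline and hide true infections. Section 12.12 also names false negatives from immunodeficiency. The net direction is not shown.

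Two further points stand in part. Table 1 only summarises the dataset; the annotated eCRF is not shown and may already hold a suitable item. Reporting by specimen type also keeps blood's contribution visible. It does not, however, separate a rise from the admission illness from a rise due to a later infection.

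**Conclusion.** The point holds as a limited one. By the protocol's own definitions, a virus acquired after the baseline samples and followed by a fourfold rise by day 25 to 31 counts as a nasopharyngeal miss, and nothing in the protocol text prevents this. It concerns hospitalised patients with paired sera only.

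The size cannot be derived from the document. Under the assumed risks and window it is about 0.2 to 1.7 patients per virus as an upper bound: possibly material when the gain is 1.5 cases, minor when it is 10.5. This is one upward component of error, not a demonstrated net bias. It is worth acting on because the remedy is cheap and depends on data that must be collected at the convalescent contact.

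**What to change.** - **eCRF:** if the annotated eCRF lacks it, add an item at the convalescent contact, where Section 12.7 already has the study nurse collect information on home visits: any new respiratory illness since enrolment, with onset date, and any positive respiratory test in the interval. Ask it also of patients who travel to the hospital for the draw.
- **Section 12.9.3.1:** keep the fourfold-rise rule for the main count. Pre-specify a sensitivity analysis of the serology and multi-specimen gain that leaves out rises in patients with a recorded new respiratory illness or positive test between the draws. Report the multi-specimen gain with and without serology.
- **Section 12.12:** name infection between the draws as a source of upward bias.

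The main count should not itself drop rises on recalled symptoms, because an untested new illness could then cancel a true index infection.

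The cost is one extra question and one extra analysis, with no added visit or sample. Asymptomatic infections between the draws are not removed, and the sensitivity count may lose a few true index infections.

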11.2 Secondary Objective(s)

2. As primary objective, stratified by:
 - Age categories: 18-49, 50-59, 60-74, 75+
 - Sex at birth
 - Time since symptom-onset categories
 - By setting (hospital, ED ward and PCC)
 - By diagnosis (upper respiratory tract infection vs. lower respiratory tract infection and pneumonia, bronchitis, bronchiolitis, etc.)
 - By common comorbidities/ chronic conditions
3. As primary objective, stratified by:
 - Vaccination status
 - RSV detection rates by RSV vaccination status (ever vaccinated or unvaccinated)
4. To assess the detection rates (%) of SARS-CoV-2 and Influenza in adult (s)ARI patients (≥ 18 years), when using multi-specimen collection compared to a single nasopharyngeal swab (overall and by additional specimen type), overall and stratified by:
 - SARS-CoV-2 detection rates by SARS-CoV-2 vaccination status (vaccinated in the last 12 months or not vaccinated in the last 12 months)
 - Influenza detection rates by Influenza vaccination status (vaccinated in the last 12 months or not vaccinated in the last 12 months).

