11.3 Exploratory Objective(s)

5. To assess the detection rates (%) of co-infections (all pathogens tested) in adult (s)ARI patients (≥ 18 years), when using multi-specimen collection compared to a single nasopharyngeal swab, overall and by additional specimen type.
 - And stratify by disease severity (setting: PCC, ED ward, hospitalization, death), if the sample size allows.
6. As primary objective, stratified by subtype or serotype (when applicable)
 - RSV detection rates by RSV subtype A and B
 - PIV detection rates by PIV serotype (1-4)
7. To assess the detection rates of Influenza, SARS-CoV-2 and other viral pathogens tested for with the RT-PCR multiplex panel in adult (s)ARI patients (≥ 18 years), when using multi-specimen collection compared to a single nasopharyngeal swab, overall and by additional specimen type.

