12.12 Limitations of the Research Methods

- The overall sample size and study period are limited, and certain respiratory pathogens or subtypes may occur infrequently, reducing the statistical power to detect associations or draw conclusions for these specific agents.
- RT-PCR offer high specificity. However, a positive RT-PCR result may not indicate causality for a respiratory infection (persistent nucleic acid from previous infection, or asymptomatic carriage).
- This study will be performed in one geographical area which may result in a limited diversity of patients when considering age, race, social economic status, chronic medical conditions and vaccinations status. The generalizability of the study might therefore be limited.
- Although the study period was selected to coincide with the high season of the pathogens of interest in the Valencia region, previous published studies have shown high seasonal variability and the circulation of the pathogens of interest might differ from the expectations.

- Despite good sensitivity and specificity of the selected serology assays, false-negative (e.g., immunodeficiency disorder) and false-positive (e.g., cross-reactivity) test results are possible.
- The second blood sample is scheduled approximately four weeks after hospital admission, when most patients are expected to have returned home. To facilitate follow-up, a nurse will be hired to visit patients at home, or transportation costs will be reimbursed. Nonetheless, some patients may still be lost to follow-up
- Timing of specimen collection: Delays between symptom onset and sample collection may result in declining viral loads, potentially affecting detection rates and diagnostic accuracy.

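### A fourfold IgG rise counts as infection in the RSV-vaccination, co-infection and subtype/serotype analyses without restriction, so vaccine responses, cross-reactive rises and inpatient-only testing can distort them

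*Protocol*

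**What the plan says.** Section 12.5.1.1 defines a laboratory-confirmed infection as a positive RT-PCR on a respiratory sample and/or "a positive serology result from paired blood samples (hospitalized patients only"). Section 12.9.3.1 sets the threshold: "Serology is considered positive for recent infection if a fourfold or greater rise in virus-specific IgG antibodies is observed between paired samples". Section 12.7 lists separate titres for RSV-A and RSV-B, hMPV-A and hMPV-B, and PIV1 to PIV4. The baseline blood sample is taken within 48 hours of admission and the second at 28 ± 3 days.

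Objectives 3 and 6 are written as the primary objective broken down further. Objective 3 asks for "RSV detection rates by RSV vaccination status (ever vaccinated or unvaccinated"). Objective 6 asks for "RSV detection rates by RSV subtype A and B" and "PIV detection rates by PIV serotype (1-4"). Objective 5 is "To assess the detection rates (%) of co-infections (all pathogens tested) in adult (s)ARI patients", under multi-specimen collection, with a breakdown by severity that uses setting as its measure if numbers allow. None of the three is limited to RT-PCR.

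For influenza, SARS-CoV-2 and the other panel targets, Section 12.5.1.1 states "There will be no results for these additional pathogens on the blood samples". Section 12.12 concedes for serology that "false-positive (e.g., cross-reactivity) test results are possible", but no analysis rule follows. Section 12.9.1 expects 150 patients with serology and calls their analysis exploratory.

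**The concern.** A fourfold IgG rise shows that antibody increased between two dates. It does not show what caused the increase, and with related antigens it does not reliably show which subtype or serotype was responsible. An overall detection rate can absorb some of that uncertainty. The three inherited analyses are more exposed because their questions coincide with the weak points of the assay: whether the patient was vaccinated, which subtype was present, and whether there was more than one pathogen.

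At stake is whether the RSV results by vaccination stratum, the subtype and serotype distribution, and the co-infection rate by setting describe infections or partly describe how and where antibody was measured.

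**Working it through.** **1. From rule to analysis.** The outcome definition (12.5.1.1) admits serology alone. The threshold (12.9.3.1) has no exception for recent vaccination or for simultaneous rises on several titres. Objectives 3 and 6 take over the primary outcome by their wording. Objective 5 covers every pathogen tested under multi-specimen collection. Serology-only positives for RSV, hMPV and PIV therefore enter all three.

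**2. Who is affected.** Inputs from 12.9.1: 150 patients with serology, about 450 inpatients, 624 ED and PCC patients, total 1,074.
- Share of all patients: 150/1,074 = 14.0%.
- Share of inpatients: 150/450 = 33.3%.
- Share of ED and PCC patients: 0/624 = 0%, since Table 2 shows no blood collected there.

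**3. Objective 3, vaccination.** No exclusion criterion in 12.3.3 covers recent vaccination. If a patient was vaccinated against RSV shortly before admission, or between the two samples, the vaccine response can meet the threshold. Conversely, a high titre from earlier vaccination can make a true fourfold rise less likely. Both errors depend on vaccination, the stratifying variable. Section 12.5.2 collects covariates at baseline, so a patient vaccinated between the samples could also be recorded as unvaccinated and RSV-positive. The net direction is therefore unknown.

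The protocol gives no frequency for vaccination in this window. If a fraction v of the 150 were vaccinated in it and all rose fourfold, spurious RSV positives = 150 × v. For an assumed v of 0.5% to 5%, this is 150 × 0.005 = 0.75 to 150 × 0.05 = 7.5 patients.

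**4. Objectives 5 and 6, cross-reactivity.** No rule says how rises on both RSV-A and RSV-B, or on several PIV titres, are assigned, or whether two subtypes or serotypes of one virus count as co-infection. If a true infection at prevalence p also produces a rise on a related titre with probability c, extra calls = 150 × p × c. Section 12.9.1 uses a generic baseline incidence of 1%–7% and a doubling, giving p of 2%–14%. With an assumed c of 10% to 50%, extra calls run from 150 × 0.02 × 0.10 = 0.3 to 150 × 0.14 × 0.50 = 10.5. True positives over the same range of p are 150 × 0.02 = 3 to 150 × 0.14 = 21. This assumes every true infection also shows its own serological rise.

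**5. Objective 5, setting.** This part needs no assumed error rate. Take an inpatient with paired sera and a PCC patient, each with one virus found by RT-PCR and an RSV infection missed by every respiratory specimen. The inpatient can be classed as co-infected through serology; the PCC patient cannot. Even a perfectly accurate assay would therefore raise co-infection only in the hospital stratum, and only through RSV, hMPV or PIV.

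**The case against.** The strongest reply is that this is containable and partly contained already. The serology analysis is labelled exploratory, results are to be read by specimen type, blood has its own denominator, cross-reactivity is disclosed, and the SAP, which is not shown, may settle evaluability windows and multi-titre rises. Much of this is fair: the window length and the handling of simultaneous rises can sit in the SAP. But the outcome definition is fixed in the protocol. The exploratory label there is tied to limited power, and nothing keeps serology-only positives out of the overall results for objectives 3, 5 and 6.

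A second reply is that excluding blood altogether would discard true serology-only infections and weaken objectives meant to show what each specimen adds. That stands, and is a reason to show both versions.

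Three stronger readings are tempting but unsupported.
- A reader might infer that vaccine antibody as such is counted as infection. A standing titre does not meet a fourfold-rise rule; only a response still developing around or between the samples could. The vaccine problem is also confined to RSV, since the influenza and SARS-CoV-2 strata of objective 4 have no blood results.
- A reader might assume 1%–2% independent false rises per titre, obtain 1 − 0.99⁴ = 3.9% to 1 − 0.98⁴ = 7.8% false PIV positives, and set these against true PIV at 1%–7%. The error rate has no source in the protocol, independence conflicts with cross-reactivity, and the result measures virus-level false positives rather than subtype misassignment or vaccination bias. The 1%–7% range is a generic baseline incidence, not a PIV rate.
- A reader might expect a biased vaccine-effect estimate. Objective 3 asks for detection rates within strata; the protocol states no vaccinated-versus-unvaccinated test or effect estimate.

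**Conclusion.** The point holds for the roughly 150 inpatients with paired sera, in one secondary objective (3) and two exploratory ones (5 and 6). As written, a vaccine response near or between the samples can count as RSV infection, a cross-reactive rise can count one infection more than once, and serology can raise co-infection only among inpatients. The third follows from the sampling scheme alone. The first two depend on rates that the protocol does not give. The ranges in the working (0.75 to 7.5 and 0.3 to 10.5 patients) are illustrations under stated assumptions, not estimates. They show only that the effect could be negligible or could be of the same order as the true positives in this subgroup. RT-PCR results in the full sample are not affected.

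**What to change.** For objectives 3, 5 and 6, state in the protocol that the main outcome definition is RT-PCR on respiratory specimens. Show serology-inclusive results separately, at virus level (RSV, hMPV, PIV), among patients with paired sera only.

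Treat RSV serology as not evaluable when the RSV vaccination date falls between the two samples or within a pre-specified window before the baseline sample. The study team should choose and justify that window in advance; the protocol offers no basis for a particular length. Table 1 already collects the vaccination date, but the registry look-up must cover the period up to the convalescent sample.

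Cost: protocol and SAP wording; a few serology-only infections leave the main version of three analyses but stay visible in the separate presentation; and the registry look-up is extended for patients with a second sample, a small addition to data collection. RT-PCR on the required specimens keeps the planned sample of about 1,074, so the planned number of patients is not reduced.
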